2. Residual blood that would otherwise be wasted from a clinically obtained sample will be collected and used for testing for biomarkers of neuronal injury (s100b and NSE). These samples will be obtained at the following 5 intervals; the pre-operative setting for baseline, post-operatively after bypass, at post-op hour 24, at post-op hour 48 and at post-op hour 72. [name], Research Program Director of the BioBank and Research Laboratory Services (RLS) at Maine Medical Center Research Institute has kindly agreed to assist with technical support for the processing of the s100b and NSE testing. The s100b testing is a serum ELISA test run on a kit provided by Millipore™. This test requires 100µL of serum per sample to be tested. This ELISA may be run on a sample that has been previously frozen. The NSE test is also run on serum and is an ELISA test requiring 100µL of serum that may also be used on a frozen stored specimen. The company providing the NSE sample kit is R&D Systems. The stored samples will then be run in batches once the full collection period is complete. The collection of the samples and the handling of samples will be facilitated by the PI and [name], research

coordinator participating in the project (please see the attached letter of support from [name], VP Neuroscience Service Line who is funding the research coordinator position).

3. Bayley Infant Scales of Development (Bayley 3) will be performed between age 9 months and 2 years. The testing will be performed by a physical therapist who assesses fine and gross motor indices and by a Master's level psychologist who assess both the cognitive and language development components. Severe developmental disability will be defined as a Bayley Mental Development Index score that is 2 standard deviations below the mean score (eg. below 70)⁵. Moderate developmental disability will be defined as a Bayley Mental Development Index score that is 1 to 2 standard deviations below the mean score (eg. below 70-84)⁵. The parents of research subjects will have the opportunity to meet with a member of the developmental assessment team to review results of the testing.

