Data will be collected at the bedside and through chart review. A study ID number will be assigned to each infant and study documents will all use this ID number to combine data. Identifiable data will be stored separately. Preoperative (baseline) variables including gender, age in months and type of congenital heart lesion will be collected. A baseline s100b and NSE will also be considered pre-operative variables. Intraoperative variables including aortic cross clamp time, cardiopulmonary bypass time, lowest temperature during surgery, time for rewarming on bypass in all 3 groups and s100b and NSE at the completion of cardiopulmonary bypass will be collected. Postoperative variables include temperature, heart rate, blood

pressure, presence or absence of an arrhythmia such as JET, pressor use, frequency of transfusions, hours of intubation, coagulation dysfunction, frequency and type of infection and presence or absence of subcutaneous fat necrosis for 48 hours after surgery. S100b and NSE will be compared at the 4 post-operative time points as well.

Success of randomization will be assessed by comparing baseline characteristics in the two treatment groups; we acknowledge that randomization may not be entirely effective with such a small sample size and we will examine the data for biases to be considered in interpreting our findings. For this safety study, primary outcomes will be composite outcomes and will include the frequency of serious adverse events as well as the frequency of any adverse events (see Table 1) and will be compared among treatment groups using chi square tests or Fisher's exact tests, as appropriate. The frequency of individual adverse events such as hemodynamic compromise, arrhythmia, coagulopathy, infection, hyperthermia and subcutaneous fat necrosis will also be examined. Biomarkers (s100b and NSE) will be examined using a repeated measures analysis of variance, with the time * treatment interaction serving as the hypothesis test.

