Stroke or seizures	Ischemic or hemorrhagic stroke OR status epilepticus OR clinical or electrographic seizures
Moderate Adverse Events	Reported to DSMB within 48 hours of occurrence
Bradycardia	Clinically significant heart rate <100 bpm for >30 minutes*
Tachycardia	Clinically significant heart rate > 160 bpm for 30 minutes*
Arrhythmia (JET)	Any occurrence of JET(Junctional ectopic tachycardia) OR other arrhythmia
Hypotension	Systolic BP< 70 mm Hg OR Diastolic BP< 30 mm Hg *
Coagulopathy	INR > 2.2 OR PTT > 74 seconds Thrombocytopenia with platelets < 50,000 Chest tube output more than 5 cc/kg/hr OR 40 cc/kg in an 8 hour shift
Leukopenia	White blood cell count < 4,000
Other adverse Events	Reported to DSMB within 7 days
Hypertension Pressor Use Days of intubation Infection Subcutaneous fat necrosis	Systolic BP > 100 mmHg OR Diastolic BP > 80 mmHg* Treatment with more than 2 pressors for more than 7 days Intubated for longer than 5 days Occurrence of urinary tract infection, pneumonia OR other wound infection Any occurrence

*resulting in hemodynamic compromise and/or need to administer medications to support heart rate and/or blood pressure

Stopping Rules: DSMB has the responsibility of pausing or stopping the trial in the case of 1) any serious adverse event probably or definitely related to study intervention OR 2) two or more unexpected or unanticipated adverse events of same or similar type

Adequacy of sample: We aim to enroll 30 infants and randomize 15 to the standard of care and 15 to the experimental group. With 15 infants in each group, we have determined that we will not have the necessary power to permit definitive analysis of the results, but will use these preliminary data to establish whether or not the treatment is safe and well-tolerated for the design of future, larger adequately powered trials.

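### The planned repeated measures ANOVA for S100b and NSE has no rule for missing samples and usually keeps only fully sampled infants; a mixed model on all observed post-operative samples would avoid that loss

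*Combined protocol and SAP*

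**What the plan says.** The biomarker analysis in the ANALYSIS section is one sentence: "Biomarkers (s100b and NSE) will be examined using a repeated measures analysis of variance", "with the time * treatment interaction serving as the hypothesis test". The version of the method, the scale of measurement, the covariance or sphericity treatment and the handling of a missing sample are not stated.

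Sampling is described under Standard of care group, second deviation from routine care, and the Experimental group section applies the same monitoring to the other arm. The source is opportunistic: "Residual blood that would otherwise be wasted from a clinically obtained sample will be collected". On timing, "These samples will be obtained at the following 5 intervals": before surgery, after bypass, and at 24, 48 and 72 hours. For S100b, "This test requires 100µL of serum per sample to be tested", and the NSE assay needs the same volume. Assays are run in batches after collection has ended.

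On baseline, the ANALYSIS section says "A baseline s100b and NSE will also be considered pre-operative variables" and "S100b and NSE will be compared at the 4 post-operative time points as well". This favours four repeated measures with baseline set apart, but the role of baseline in the model is not stated.

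Adequacy of sample gives the size: "We aim to enroll 30 infants and randomize 15 to the standard of care and 15 to the experimental group". It concedes that power is inadequate. Anticipated outcomes makes the biomarkers secondary and expects only a trend.

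**The concern.** Classical repeated measures ANOVA, univariate or multivariate, needs a complete row for each infant. One missing value removes that infant's other values too.

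The documents give reasons to expect some gaps:

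- No dedicated research draw is described. Each time point depends on enough serum being left for two assays from a small infant.
- Routine monitoring commits to daily kidney function tests for 48 hours only and to early removal of central lines. Coagulation screening is daily with no stated end. Clinical blood is therefore least certain at 72 hours.
- Because assays are batched at the end, an inadequate sample may be found when it can no longer be replaced.
- Randomization happens at consent, before surgery. An infant who later dies or cannot be weaned from bypass loses later samples, and complete-case deletion would discard any earlier ones.

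At stake is the precision of the biomarker comparison. With 15 infants per arm there is little to spare. If gaps are related to how sick the infant is, the infants left in the analysis are also a selected group.

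**Working it through.** **Inputs.** From the documents: 15 + 15 = 30 infants; four post-operative times, or five with baseline. The plan gives no power, alpha, SD, effect size or expected sample loss for the biomarkers, so it has no figure of its own to reproduce beyond that sum. Assumed: the share m of samples missing at each time point, from 2% to 20%.

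**Infants kept by a complete-case analysis.** With independent gaps, the share of infants complete at k times is (1 − m)^k.

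| m (assumed) | (1 − m)^4 | kept of 30, four times | (1 − m)^5 | kept of 30, five times |
|---|---|---|---|---|
| 2% | 0.922 | 27.7 | 0.904 | 27.1 |
| 5% | 0.815 | 24.4 | 0.774 | 23.2 |
| 10% | 0.656 | 19.7 | 0.590 | 17.7 |
| 20% | 0.410 | 12.3 | 0.328 | 9.8 |

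The five-time columns also apply if baseline enters the ANOVA as a required covariate, because an infant without a baseline value is then lost.

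**Clustered gaps.** Death, early line removal and similar causes put gaps in the same infants. Take beta-binomial missingness with within-infant correlation 0.3 (assumed). Put s = 1/0.3 − 1 = 2.333 and b = (1 − m)s. The share complete at k times is the product of (b + i)/(s + i) for i = 0 to k − 1. For m = 10%, b = 2.1, and four times give 0.900 × 0.930 × 0.946 × 0.956 = 0.757, or 22.7 of 30. At m = 2%, 5%, 10% and 20%, four times keep 28.4, 26.2, 22.7 and 16.8 infants, and five times keep 28.2, 25.7, 21.9 and 15.6.

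**Samples used if every observed value counts.** At four times there are 30 × 4 = 120 planned values. At the same four rates, 120(1 − m) = 117.6, 114, 108 and 96 are available.

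**What this could mean for power.** An illustrative simulation used 15 infants per arm, five times, lognormal values with log-SD 0.5, within-infant correlation 0.5, a peak effect of 1 SD, and an interaction F test with infant effects on the log scale, in 1,500 runs per setting. All of these are assumptions, and the test stands in for a mixed model. Power for complete cases against all available values was 65% against 77% at m = 5%, 49% against 72% at 10%, and 25% against 63% at 20%.

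**Scale, as a separate question.** In the same kind of simulation with no treatment effect and log-SD 0.5 or 0.8, the raw-scale test rejected in about 8–10% of runs at a nominal 5%, against about 4–6% on logs. Raw-scale power was not lower than log-scale power. The case for logs is therefore control of false positives under assumed skewed data. It is not a case about power.

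**The case against.** The strongest reply is that the plan is silent here, and silence is not a wrong choice. The wording does not say that incomplete infants are dropped, and it does not exclude a mixed-model fit. That stands: deletion is the usual default of the named method and is not a stated rule. It remains a reason to settle the matter in writing before the data are seen.

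A reader might go further and infer any of the following. The documents do not support them.

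- *A large share of the 30 infants will be lost.* No missing rate is given. At 2% per time point the loss at four times is about 2 infants (30 − 27.7). Several facts hold losses down: all infants have arterial lines, blood gases and coagulation tests are regular, kidney tests run daily to 48 hours, the assay volumes are small, frozen serum is accepted, and a research coordinator helps with collection. Equal loss at every time point is a simplification.
- *Raw concentrations will be analysed.* No scale is named. ANOVA can be run on logs, and no biomarker distribution is reported.
- *A mixed model would recover every infant.* It uses observed values only. Infants with no post-operative sample add almost nothing. Inability to wean from bypass is an exclusion criterion, so whether those infants are analysed at all is a separate question.
- *Faulty biomarker estimates would size the efficacy trial.* The Background describes a future trial of developmental outcome, and no section says that the biomarker results will set its size.

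Sphericity is a lesser matter: the multivariate form does not need it, and the univariate form has standard corrections.

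**Conclusion.** The concern holds in a limited form. The plan names a method that ordinarily needs complete data, pairs it with opportunistic sampling, and has no missing-sample rule. At assumed independent missing rates of 2% to 20% per time point, complete-case analysis of the four post-operative times would keep about 28 down to 12 of 30 infants, or 27 down to 10 if baseline must also be present. With clustered gaps (correlation 0.3) the four-time range is about 28 to 17. The true figure depends on a rate that the documents do not give.

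The change is worth making because it is nearly free and uses data already collected. It affects the precision of a secondary endpoint that the plan itself calls underpowered, and leaves the primary safety comparison untouched. A mixed model is valid if samples are missing at random. If loss depends on the unobserved biomarker values themselves, it does not remove the bias.

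**What to change.** In the ANALYSIS section, replace the repeated measures ANOVA with a linear mixed model for each biomarker:

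- **Data:** all observed post-operative samples.
- **Terms:** baseline value as a covariate, time, treatment and their interaction.
- **Estimation:** restricted likelihood with Kenward-Roger degrees of freedom.
- **Covariance:** unstructured, which has 4 × 5 / 2 = 10 parameters at four times. If it does not converge, use a named simpler form, for example heterogeneous compound symmetry with 4 variances + 1 correlation = 5.

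Two details follow from taking baseline out of the repeated factor. First, an infant without a baseline sample would drop out of the model (30m, or 0.6 to 6 infants over the assumed rates), so state how such infants are kept, for example by using the overall mean baseline. Second, the interaction would then miss an arm difference that is constant over the four times, so state whether the test is the joint test of treatment and interaction or the arm contrast at each time.

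As a separate sentence, specify log-transformed values. Report ratios of geometric means with 95% intervals, and the number of samples by arm and time so that the actual loss is visible. State the missing-at-random assumption.

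The cost is a few sentences and standard software. The small downside is that the covariance may need simplifying with 30 infants.

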2.1 Compare levels of serum biomarkers of brain injury in the acute post-operative setting including serum s100b and NSE (neuron specific enolase). Levels will be assessed in both groups in the pre-operative setting for baseline and

serially in the post-operative setting for 72 hours. It is hypothesized that infants in the “delayed rewarming” group will show a trend toward lower levels of biomarkers of brain injury.

[figure not shown]
2.2 Record EEG and monitor seizure frequency in infants for 48 hours following CHD surgery. Seizures, if they occur, will be treated in both groups and the duration quantified in seconds. EEG is needed primarily to rule out potential confounding effects of seizures on later developmental outcome. It is hypothesized that there will be infrequent seizures and no differences in seizure frequency or duration between groups.

2.3 Compare developmental outcomes using Bayley Scales of Infant Development (Bayley 3). Bayley testing will be performed on infants at either 6 or 12 months of age depending on the infant’s age at the time of surgery. It is hypothesized that infants in the “delayed rewarming” group will show a trend toward improved Bayley scores compared to the standard of care group.

Preliminary data:

A retrospective review of cases of congenital heart disease requiring surgical palliation was performed for cases from January 2011 to May 2014. The database was provided by [name] to [name] for the purposes of this analysis. This database is kept for quality work in [name] office. Please see the attached letter of support for this project from [name]. In this review, there were 191 surgeries performed on infants under the age of 12 months by [name] in the 41 month interval (average 4.6 surgeries per month). Some infants required multiple surgeries and therefore the total number of surgeries (191) reflects 119 individual infants. The proposed research project includes only infants undergoing cardiopulmonary bypass (CPB) for the first time. In this sample, there were 88 CPB surgeries. Ten infants had surgery requiring CPB on more than one occasion and thus eliminating repeat exposures to cardiopulmonary bypass, 76 of the 88 total surgeries would have met inclusion criteria for enrollment into this research project (1.9 infants per month or 22 per year). Anticipating a 2 year period of recruitment, there should be approximately 44 eligible infants and we will seek to enroll 30.

[figure not shown]

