In the same review from 2008-2013, fourteen infants arrived to the PICU with temperatures above 38°C, with 2 of those over 39°C and as such would be considered **hyperthermic** (see Figure 2). Of the 14 **hyperthermic** PICU arrivals, 1 died 2 weeks following surgery from heart failure. This preliminary data demonstrates a significant need for better post-operative temperature management as it is well established in the traumatic brain injury and stroke literature that **hyperthermia** is associated with worse outcomes. This preliminary data also suggests that by rewarming to 36-36.5°C according to the current institutional protocol on cardiopulmonary bypass, at least one third of infants then develop "overshoot" of their temperature beyond 37°C. This post-operative **hyperthermia** may also be corrected with use of the delayed rewarming strategy proposed in this project and as such is a potentially modifiable source of neurological injury.

MATERIALS AND METHODS

Subjects and study design: 30 infants under the age of 12 months with congenital heart disease requiring cardiopulmonary bypass surgery will be recruited for this study. The experimental treatment is “delayed rewarming” and will be defined as the cessation of rewarming on cardiopulmonary bypass at 35°C (see Figure 3). During both phases, there will be 12 hours of controlled rewarming to 36.5°C and the temperature will be maintained at 36.5 C for the 12 hours after rewarming . All types of congenital heart disease requiring cardiopulmonary bypass and intraoperative hypothermia will be considered for enrollment including (Tetralogy of Fallot (TOF), Arterioventricular canal (AV canal), Hypoplastic left or right heart (HLHS), Transposition of the Great Arteries (TGA), Truncus arteriosus (TA) and Total Anomalous Pulmonary Venous Return (TAPVR). Exclusion criteria include a pre-existing coagulopathy or cardiac lesions not requiring hypothermia and bypass and these include Atrial Septal defect (ASD), Ventricular Septal Defect (VSD), Patent Ductus Arteriosus (PDA) and Coarctation of the Aorta (Coarc). Exclusion criteria also includes the inability to wean from bypass following surgery. This is a randomized pilot study primarily assessing the safety of the delayed rewarming technique and secondarily assessing levels of serum biomarkers for neuronal injury at the 4 intervals shown below (see Figure 3).

Figure 3a: Research design for pilot

[figure not shown]
[figure not shown]

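### The plan hypothesises lower S100b and NSE levels, but its only named biomarker test is the time-by-treatment interaction, which is unsigned, has no baseline covariate and does not say whether baseline is a level of time

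*Combined protocol and SAP*

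**What the plan says.** **Hypothesis.** Specific Aim 2.1 expects that the delayed rewarming "group will show a trend toward lower levels of biomarkers of brain injury". Anticipated outcomes repeats this for both markers. Subjects and study design describes the study as "secondarily assessing levels of serum biomarkers for neuronal injury at the 4 intervals shown below".

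**Test.** The Analysis section specifies a repeated-measures ANOVA, "with the time * treatment interaction serving as the hypothesis test". It names no treatment main effect, contrast or covariate. It also says: "S100b and NSE will be compared at the 4 post-operative time points as well". No method is attached to that sentence.

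**Samples.** The second deviation from routine care, under Standard of care group, gives the schedule: "These samples will be obtained at the following 5 intervals; the pre-operative setting for baseline, post-operatively after bypass", then hours 24, 48 and 72. Specific Aim 2.1 describes a pre-operative level and then sampling "serially in the post-operative setting for 72 hours". In the Analysis section, "A baseline s100b and NSE will also be considered pre-operative variables". The same section lists the after-bypass sample among the intraoperative variables ("s100b and NSE at the completion of cardiopulmonary bypass will be collected"), yet its count of 4 post-operative times needs that sample.

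**Size and status.** Adequacy of sample gives 15 infants per arm and says the study lacks power for definitive analysis. Anticipated outcomes makes the markers secondary and says the study is not powered for them.

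**The concern.** A hypothesis of lower levels is directional and concerns the height of the curve. The time-by-treatment interaction asks whether the two curves are parallel. It spreads over 3 or 4 degrees of freedom, has no sign and yields no single estimate of how much lower the levels are.

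The result then depends on a choice the plan leaves open. If time is the 4 post-operative samples, curves that are lower throughout by a constant amount are parallel, and the named test has nothing to find. If baseline is a fifth level, the same reduction is a departure from a common starting point, and the interaction can pick it up. On either reading a significant interaction does not by itself show that levels were lower: higher levels at one time, or crossing curves, can also produce it.

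At stake is the interpretation of the biomarker result. No decision in the plan depends on this p-value, but the pilot is meant to inform a later efficacy trial, and a signed difference with an interval serves that better than an omnibus p-value.

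**Working it through.** The plan gives no effect size, SD, within-infant correlation or alpha for the markers, so there is no figure of its own to reproduce.

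**Inputs.** From the plan: 15 per arm, 1 baseline and 4 post-operative samples. Assumed: effect 0.8 SD on the analysis scale, SD 1, compound symmetry with correlation ρ = 0.3/0.5/0.7, two-sided 0.05, complete data. Results are given in that order of ρ.

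**Interaction.** With k levels of time and between-arm differences d at each level, λ = (15×15/30) × Σ(d − mean d)² / (1 − ρ), on k−1 and 28(k−1) degrees of freedom.

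- *4 levels, sustained reduction.* d = 0.8 throughout, so Σ = 0 and λ = 0. Power is 5/5/5%.
- *5 levels, sustained reduction.* d = 0 at baseline and 0.8 at the other four, mean 0.64. Σ = 0.64² + 4 × 0.16² = 0.512, and λ = 7.5 × 0.512/(1 − ρ) = 5.49/7.68/12.80 on 4 and 112 df. Power is 42/56/81%.

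**Baseline-adjusted mean of the 4 post-operative samples (ANCOVA, 27 df).** The mean has variance (1 + 3ρ)/4, and adjustment removes ρ². The residual variance is 0.475 − 0.09 = 0.385, 0.625 − 0.25 = 0.375, and 0.775 − 0.49 = 0.285. The standard error of the difference is about √(residual × 2/15) = 0.227/0.224/0.195, slightly more after allowing for chance baseline imbalance. For a difference of 0.8, power is 92/92/97%. Without the covariate it is 87/76/67%, so much of the gain at higher ρ comes from the baseline sample.

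**Other effect shapes.** The difference in the 4-sample mean is 0.8 for a sustained effect, 0.6 if it starts at 24 h, 0.4 if it fades linearly from 0.8 to 0 or is present at 24 and 48 h only, and 0.2 if confined to the after-bypass sample. The same formulas give:

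| Effect | Interaction, 4 levels | Interaction, 5 levels | Adjusted 4-sample mean |
|---|---|---|---|
| Sustained | 5/5/5% | 42/56/81% | 92/92/97% |
| From 24 h on | 43/58/82% | 60/76/95% | 71/72/83% |
| Fading 0.8 to 0 | 33/45/68% | 39/54/79% | 39/40/49% |
| 24 and 48 h only | 56/72/92% | 60/76/95% | 39/40/49% |
| After-bypass only | 43/58/82% | 42/56/81% | 13/14/16% |

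**Weak baseline.** Suppose baseline correlates only 0.2 with later samples and the effect is sustained. The residual variance is then (1 + 3ρ)/4 − 0.04 = 0.435/0.585/0.735. The adjusted mean has 88/77/68% power, against 36/40/42% for the 5-level interaction with Greenhouse-Geisser correction.

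**Scale.** The 5% needs a reduction constant on the scale analysed. A constant 33% reduction analysed on raw values, with levels falling 2-fold or 4-fold over the 4 samples (log SD 0.5, ρ 0.5, Greenhouse-Geisser), gives the 4-level interaction 14% or 30% power.

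**The case against.** The strongest defence is that baseline is naturally a level of time. Aim 2.1 describes one series from baseline to 72 hours, and the schedule lists baseline first of five. On that reading the interaction is the conventional test of differential change from baseline, and it uses the baseline value. This stands: the test is then valid, and what remains is its lack of sign and its lower efficiency for a sustained effect. But the Analysis section classes baseline with the pre-operative variables and speaks of 4 post-operative times, so the text does not settle the matter.

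A reader might infer three stronger things, none of which the documents support:

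- *That the planned test cannot detect lower levels.* This holds only if baseline is not a level of time and the reduction is constant on the analysis scale.
- *That no comparison of levels is planned, or that the sampling times are missing or contradictory.* A comparison at the 4 post-operative times is promised; it lacks a test and an adjustment. The schedule is fully stated, and 4 post-operative samples plus baseline make 5. The 4 intervals in the design section refer to a figure not visible here.
- *That the test should be confined to 24–72 h, because the after-bypass sample precedes the 12-hour rewarming.* That sample follows the randomised stop of on-bypass rewarming at 35°C (Experimental group), so it is an outcome from a period when the arms already differ. Dropping it would leave 18/19/24% power for the fading effect.

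It is also fair that the interaction wins for several transient shapes, that the documents do not say how long an effect would last, and that the markers are secondary in a study that expects only a trend. These points limit the weight of the concern. They do not align the test with the hypothesis.

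**Conclusion.** The mismatch is established from the text: the hypothesis is about level, the only named test is about shape, the collected baseline is not a covariate, and the levels of time in the ANOVA are not stated. Its size depends on the missing statement. With 4 levels, power equals alpha for a constant reduction; with 5, the cost for a sustained reduction is 42/56/81% against 92/92/97%. These figures rest on an assumed 0.8 SD effect, compound symmetry, complete data and a sustained effect; for an effect that fades or is brief the ordering can reverse. The practical consequence is confined to reading the biomarker result: a non-significant interaction may not mean similar levels, and a significant one does not say that levels were lower or by how much. The change is worth making because it is nearly free, not because the trial's main conclusions are at risk.

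**What to change.** For each biomarker, fit a repeated-measures model with the 4 post-operative samples of the stated schedule as outcomes, the baseline marker as covariate, and treatment, time and treatment-by-time as terms. Use the log scale if values are skewed, and write that rule down before the stored samples are assayed.

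Make the hypothesis test the baseline-adjusted treatment difference averaged over all 4 post-operative samples, with a 95% CI. Report each baseline-adjusted per-time difference with its CI, and the treatment-by-time interaction, as supportive. Do not restrict the average to 24–72 h, and do not use the after-bypass sample as a covariate, since it follows randomised treatment.

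The cost is wording only: the baseline marker and every sample are already planned. The downside should be stated openly. The average has less power than the interaction for some transient effects, most clearly one confined to the after-bypass sample (13/14/16% against 42–43/56–58/81–82%). Such effects stay visible in the supportive results.
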